7.2.2 Patient Selection

7.2.2.1 Inclusion Criteria

Four cohorts will be created based on healthcare setting and type of steroid use. Their eligibility criteria being described below (using Covid-19 catch-all definition Section 7.3.1):

Ambulatory prevalent user

- Have at least 365 days of continuous observation time prior to cohort entry
- Have a glucocorticoid (oral or parenteral) exposure in the 120 days prior to diagnosis date (unrelated to COVID-19 diagnosis)
- Have a positive PCR test for SARS-CoV-2 (labCOVID-19) or a confirmed COVID-19 diagnosis (diagCOVID-19)
- Have no hospitalizations in the 30 days prior to or on index

Ambulatory naive user

- Have at least 365 days of continuous observation time prior to cohort entry
- Have no glucocorticoid (oral or parenteral) exposure in the 120 days prior to index (unrelated to COVID-19 diagnosis)
- Have a positive PCR test for SARS-CoV-2 (labCOVID-19) or a confirmed COVID-19 diagnosis (diagCOVID-19)
- Have no hospitalizations in the 30 days prior to or on index

Hospitalized prevalent user

- Have a glucocorticoid (oral or parenteral) exposure in the 120 days prior to index (unrelated to COVID-19 diagnosis)
- Have a positive PCR test for SARS-CoV-2 (labCOVID-19) or a confirmed COVID-19 diagnosis (diagCOVID-19) (index date)
- Are hospitalized 30 days prior or after diagnosis index date
- Have no intensive services in the 30 days prior to or on index

Hospitalized naïve user

- Have no prior exposures to glucocorticoids in the 120 days prior to index
- Have a positive PCR test for SARS-CoV-2 (labCOVID-19) or a confirmed COVID-19 diagnosis (diagCOVID-19)
- Are hospitalized 30 days prior or after diagnosis index date
- Have no intensive services in the 30 days prior to or on index

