7.7.2 Glucocorticoid prescribing patterns (primary objective 1)

Prescribing patterns of systemic glucocorticoids for the treatment of COVID-19 will be summarized by the four cohorts (section 7.2.2) and by subgroups of special interest (section 7.2.4) and the description will include time to initiation of glucocorticoid treatment (from COVID-19 diagnosis), duration of treatment, route of administration, daily dose at start, cumulative dose and duration of

treatment received post COVID-19 diagnosis, see section 7.3.2 for details regarding calculation of exposure parameters .

Frequency of concomitant use of other medications and invasive/non-invasive respiratory support at COVID-19 diagnosis index date and during follow-up will also be presented.

The time to systemic glucocorticoid initiation from COVID-19 diagnosis will be modelled as a time-to-event outcome using the Kaplan-Meier (KM) estimator. The patient follow-up from COVID-19 diagnosis date until systemic glucocorticoid treatment index date will be included in the KM analysis, with start of systemic glucocorticoid therapy being considered a ‘failure’ event. This KM analysis will be stratified by route of systemic glucocorticoid administration (oral vs intravenous). The KM survival function curve (95% CI) and summary statistics of 25th percentile, median, 75th percentile of time to event (in days) will be provided. The survival function within each stratification will be compared using log-rank test.

A time series graph will be used to investigate changes in prescribing patterns over calendar time. Monthly and quarterly incidence steroid incident use will be plotted against time from January 2020 until study end. Key dates (such as Recovery trial) should be highlighted on this graph to allow differentiation between time periods. A formal before /after analysis is not proposed. Results will be stratified per country and per database.

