7.7.3 Patient characteristics (secondary objective 1)

Summary descriptive statistics will be presented by the four cohorts (section 7.2.2) and *described both at diagnosis and treatment index dates in each cohort*. The following will be described at diagnosis date and also treatment index date: patient demographics and clinical characteristics. Where available, a description of COVID-19 illness onset (time to diagnosis), associated symptoms and time to hospitalization for COVID-19 infection will be presented.

Data will be further stratified by subgroups of special interest (see section 7.2.4).

7.7.4 Estimation of incidence of study adverse events of interest and disease outcomes (secondary objectives 2 and 3)

The crude incidence rate of the individual outcome relevant to each sub-cohort reported during person-time treated for each exposure group will be calculated. The crude person-time from relevant index date will be calculated for the following groups:

- Use of systemic glucocorticoids without other treatments for COVID-19 (drug and respiratory support)
- Use of systemic glucocorticoids plus other treatments for COVID-19 (drug and respiratory support)
- Only other treatments and respiratory support with no steroids
- No specific treatments for COVID-19 infection (other concomitant treatments are allowed are allowed)

Only the earliest eligible treatment is considered, and for patients who switch to another treatment (including switch to another glucocorticoid), their follow-up is censored at date of switching. The number and reasons for patients censoring will be reported.

We will calculate both, the incidence proportion and the incidence rate. The numerator for both (risk and rate) will be comprised of counts of incident events of interest during the person-time as defined above recorded during each cumulative interval and summed to reflect the cumulative count for the interval.

The crude cumulative incidence rate will be calculated according to the formula:

$$\frac{\text{Total number of patients on Rx with first event during cumulative interval of interest}}{\text{Total person-time at risk (days)}} \times 100$$

The crude incidence proportion will be calculated according to the formula:

$$\frac{\text{Total number of patients on Rx with first event during cumulative interval of interest}}{\text{Total population at risk at start of study period}} \times 100$$

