7.9 Limitations of the Research Methods

7.9.1 Study design limitation

COVID-19 diagnosis misclassification – the diagnosis of COVID-19 in absence of confirmatory test has a high likelihood to be misclassified as the disease symptoms are unspecific. This misclassification is more likely for patients treated in primary care, e.g., those with milder symptoms. In addition, with regards to the availability of results of PCR test for SARS-CoV-2, this is currently available in only one database (SIDIAP).

- **Mitigation:** Different definitions will be explored and compared as part of objective 4. We will base the main definition on definite diagnosis not on symptoms only and supplement with confirmatory tests when available

Confounding by indication and severity may occur when the different treatments are prescribed depending upon the physician's assessment of the patient's health status in relation to the outcome of interest. The risk of this confounding is high due to glucocorticoids being indicated in severe COVID-19 cases only and therefore correlated with the increase in severity.

- **Mitigation:** No comparative analysis will be performed. This confounding needs to be considered when interpreting the incidence rates obtained.

Selection bias occurs when there is a selective recruitment into the study of subjects that are not representative of the population intended to be studied, so that the association between exposure and outcome of interest is different in the included and excluded population.

- **Mitigation:** Minimal exclusion criteria will be used. In addition, we have included data sources with large or whole national coverage and both ambulatory and hospital setting.

Exposure to glucocorticoids in hospital setting might be underrepresented as glucocorticoid might be captured only as ward stock and not as individual dispensation.

On-treatment exposure classification was considered suitable for this study in order to facilitate comparison with clinical trials results. However, this way of classifying exposure does not consider subsequent treatments and might miss a deterioration of disease.

The **short duration of follow-up** will allow only the capture of acute adverse events.

Prescribing patterns of corticosteroids over time

Due to the short study period (1 year) any time series analysis cannot be undertaken, and the observed trends cannot be confirmed.

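### The hospital cohorts exclude patients with intensive services by the diagnosis date, and this exclusion carries into the primary objective and secondary objectives 1 to 3, although only one outcome evidently needs it

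*Protocol*

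**What the plan says.** Section 7.2.2.1 of the protocol lists the same two conditions for the prevalent and the naive hospital cohort: "Are hospitalized 30 days prior or after diagnosis index date" and "Have no intensive services in the 30 days prior to or on index". Index here is most naturally the diagnosis index date, because the hospitalized prevalent list attaches that label to the PCR or diagnosis criterion. Both ambulatory cohorts require that patients "Have no hospitalizations in the 30 days prior to or on index".

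The analysis sections work on these cohorts. For the primary objective, Section 7.7.2 states: "Prescribing patterns of systemic glucocorticoids for the treatment of COVID-19 will be summarized by the four cohorts". For secondary objective 1, Section 7.7.3 states: "Summary descriptive statistics will be presented by the four cohorts". Section 7.7.4 computes the incidence analyses for objectives 2 and 3 within the same sub-cohorts. Section 7.3.4 lists intensive services as one of five severity outcomes in the hospitalized cohorts.

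Section 7.7.2 also promises that the frequency of "invasive/non-invasive respiratory support at COVID-19 diagnosis index date and during follow-up will also be presented". Section 7.9.1 describes "glucocorticoids being indicated in severe COVID-19 cases only" as a source of confounding.

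**The concern.** Section 6.2 states the hospital population of the primary objective simply as patients in hospital care. The entry condition narrows it to patients who had no intensive services in the 30 days up to and including diagnosis. This is selection on severity, which the protocol itself links to glucocorticoid prescribing. Section 5.0 cites a larger mortality reduction with dexamethasone in ventilated patients (35%) than in patients on supplemental oxygen (20%), so use in the ventilated group is of evident interest.

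Two things are at stake. First, the group is lost from the glucocorticoid description. Section 7.5 says only one database observes hospitalized patients, so no other source supplies them. Second, the hospital estimates of use and of the other outcomes describe a different population from the one named. If glucocorticoid use differs between excluded and retained patients, the reported proportion treated is shifted. No reason for the condition is given, and Section 7.9.1 does not list it as a limitation.

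**Working it through.** The protocol states no figure on this point that could be reproduced; Section 7.5 gives only patient counts. The check is therefore textual, with an illustration of size.

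**1. Where the excluded patients go.** An inpatient with intensive services by diagnosis fails the hospital condition. The same patient, being in hospital by index, also fails the ambulatory condition. He or she enters none of the four cohorts.

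**2. Which analyses are affected.**

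| Analysis | Population | Does it need the condition? |
|---|---|---|
| Primary objective (7.7.2) | the four cohorts | No |
| Secondary objective 1 (7.7.3) | the four cohorts | No |
| Objective 2, adverse events (7.7.4) | the same sub-cohorts | No |
| Objective 3, intensive services (7.3.4, 7.7.4) | the same sub-cohorts | Yes, to define who is at risk |
| Objective 3, death, discharge, VTE/PE, DIC | the same sub-cohorts | No |
| Objective 4 (7.7.6) | sampled from the study population | Not affected |

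Section 7.1 says that cohorts will be used differently by objective, as set out in the analysis section. Sections 7.7.2 to 7.7.4 lift this condition for none of them.

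**3. Who stays in.** The condition stops at the diagnosis date. Patients who reach intensive services afterwards are retained, and their respiratory support during follow-up is described. Oxygen therapy (concept 4239130, Appendix 1 section 6.1) is not in the intensive-services list (section 4.3), so patients on oxygen alone are retained too.

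**4. Size, under assumptions.** The documents give neither the share excluded, x, nor glucocorticoid use in excluded (p1) and retained (p0) patients. With N of about 2,000 hospital patients (Section 7.5):

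- number excluded = N·x
- shortfall in the proportion treated = x·(p1 − p0)
- share of hospital glucocorticoid users lost = x·p1 / [x·p1 + (1 − x)·p0]
- 95% CI half-width = 1.96·√[p0(1 − p0) / (N(1 − x))]

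| x | p0 | p1 | Excluded | Shortfall (points) | CI half-width (points) | Users lost |
|---|---|---|---|---|---|---|
| 1% | 30% | 50% | 20 | 0.2 | 2.0 | 1.7% |
| 5% | 30% | 80% | 100 | 2.5 | 2.1 | 12.3% |
| 10% | 30% | 50% | 200 | 2.0 | 2.1 | 15.6% |
| 10% | 50% | 80% | 200 | 3.0 | 2.3 | 15.1% |
| 15% | 30% | 80% | 300 | 7.5 | 2.2 | 32.0% |

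The last row is 0.15 × (80 − 30) = 7.5 points, and 0.12 / (0.12 + 0.255) = 32%. With p1 = p0 = 50% the shortfall is 0 at any x. If p1 were below p0, the shift would reverse.

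**5. The code list.** Steps 1 to 4 take intensive services to mean ventilation, ECMO and tracheostomy. Appendix 1 section 4.3 also lists concepts 262 and 9201. These are the two concepts that make up hospital admission in section 4.1. If any single listed code qualifies, the condition removes everyone admitted in the 30 days before or on index. Only patients admitted 1 to 30 days after diagnosis would then remain, and the half of the hospitalization criterion that allows earlier admission would be empty. The appendix does not say whether these codes must occur together with a procedure code.

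**The case against.** The best defence is that the design is deliberate and symmetrical. Ambulatory patients start outside hospital, hospital patients start outside intensive services, and in each setting the next level of care is an outcome. That is a recognisable design, and the protocol gives no reason that rules it out. It explains the condition for the intensive-services outcome, however, and not for describing drug use or for the other outcomes.

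Section 7.7.1 promises a STROBE diagram with the proportion and summary characteristics of excluded patients. This stands: readers should see how many were removed and what they look like. It does not supply their glucocorticoid type, timing, route, dose or duration.

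Some stronger readings are tempting, and the documents do not support them:

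- **That the plan drops severe patients as a whole.** Severe is not the same as being in intensive services by diagnosis. Later escalation and oxygen therapy are retained.
- **That the plan contradicts itself outright.** Section 7.9.1 says "Minimal exclusion criteria will be used", and minimal does not mean none. The invasive-support row at diagnosis will be nearly empty in the hospital cohorts, but the rest of that planned table is informative.
- **That use, early initiation, intravenous use and mortality are certainly understated.** No passage gives these by intensive-services status in the hospital database. That database locks in April 2020 (Table 1), while the cited dexamethasone trial report carries a June 2020 preprint identifier. The trial cannot show that ventilated patients in this database were treated more often.

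**Conclusion.** The point holds in a limited form. The condition is written at cohort level, is unexplained, and reaches the primary objective and secondary objectives 1 to 3; objective 4 is untouched. As planned, the hospital results apply to patients without intensive services in the 30 days up to and including diagnosis, and glucocorticoid use in the excluded group cannot be reported from the only hospital database.

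The effect on the overall proportion treated is unknown in size and direction. It is zero if use is equal in both groups. Over the assumed range (1–15% excluded, use of 50–80% against 30–50%) it runs from 0 to 7.5 percentage points. That can lie well inside or well beyond a sampling half-width of about 2.0 to 2.4 points. These figures rest on the narrow reading of intensive services and do not describe the plan if the Appendix 1 list is applied literally. This is a worthwhile and cheap improvement, not a demonstrated bias of known size.

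**What to change.** 1. Remove the intensive-services condition from the two hospital cohort definitions in Section 7.2.2.1.
2. State it in Sections 7.3.4 and 7.7.4 as the at-risk condition for the intensive-services outcome only, naming which of the two index dates in Section 7.2.3 it refers to.
3. For the primary objective, secondary objective 1 and all other outcomes of objectives 2 and 3, report the hospital cohorts overall and by intensive services at diagnosis (yes/no). The stratum without intensive services gives the results now planned, so nothing is lost.
4. Reconcile Appendix 1 section 4.3 with section 4.1. Either take concepts 262 and 9201 out of the intensive-services list or state that they count only together with a procedure code. The appendix calls its lists examples, so the final list should be fixed before extraction.

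The cost is a wording change and one more stratum in the hospital tables, with no new data. The drawback is small cells in the intensive-services stratum: under the assumed 1–15%, about 20 to 300 of some 2,000 hospital patients, before any split by naive and prevalent use.

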7.2.2.2 Exclusion Criteria

Missing age or sex

7.2.3 Follow-up

Two index date definitions will be applied as appropriate for each objective.

- Diagnosis index date is defined as a positive PCR test for SARS-CoV-2 (labCOVID-19) or a confirmed COVID-19 diagnosis(diagCOVID-19) whichever is the earliest.
- Treatment index date is defined as start of first systemic glucocorticoid treatment episode specifically for the treatment of COVID-19, irrespective of whether the patient is a prevalent or naïve user.

Follow up for all patients will begin from the index date until they experience the outcome of interest (endpoint, depending on the objective) or until cohort exit (date of censoring). The patients will be followed up for maximum 90 days or until censoring occurs, censoring criteria are:

- death
- patient exit (deregister) from a contributing data provider (GP practice)
- end of the database's data collection
- end of study period (latest data cut-off)

The lookback window for evaluating risk factors, medical history is 365 days and will be applied only to outpatient cohorts.

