Variables	
COVID-19 Case Definition
 
 • Main analysis: Catch-all definition based on the earliest of a first diagnosis confirmed for COVID-19 or first SARS-CoV-2 positive PCR test 
Secondary Objective 4 alternative definitions: Diagnosis confirmed (diagCOVID-19), laboratory confirmed (labCOVID-19), symptomatic COVID-19 and suspected COVID-19 cases
 
Exposure (based on prescription data)
 
 • Glucocorticoids used in COVID-19 indication glucocorticoid (dexamethasone, prednisolone, prednisone, methylprednisolone or hydrocortisone) • Glucocorticoid for pre-existing conditions, described by metrics such as proportion of days covered in lookback period and recent use of medication based on prescription records. • Other COVID-19 treatments (e.g., antiviral, antibiotic, statin therapy) • Respiratory support 
These will be further characterized using specific criteria and formula for dose and duration.
 
For secondary objectives 2 and 3 where the index date is based on treatment, the treatment exposure groups will be categorized as follows:

- Use of systemic glucocorticoids without other treatments for COVID-19
- Use of systemic glucocorticoids plus other treatments for COVID-19
- Only other treatments and respiratory support with no systemic glucocorticoids
- No specific treatments for COVID-19 infection

Outcomes (Secondary objectives 2 and 3)

- Adverse events: composite cardiovascular events, hypertension, arrhythmia, gastritis, gastric ulcer, GI bleed, psychosis, myopathy, hyperglycaemia and any bacterial viral, fungal and parasitic infection
- Disease severity:
 - Ambulatory: Hospital admission, venous thromboembolism or pulmonary embolism, disseminated intravascular coagulation, death of any cause
 - Hospital: Intensive services as an outcome in inpatient cohorts (including mechanical ventilation and Extracorporeal membrane oxygenation (ECMO)), venous thromboembolism or pulmonary embolism, disseminated intravascular coagulation, discharge from hospital, death of any cause

Demographic and clinical variables: age, sex, month of diagnosis, comorbidities

Data sources

Ambulatory:

- Belgium, France, Italy – Longitudinal Patient Database (IQVIA)
- Germany – Disease Analyser (IQVIA)
- United Kingdom – IQVIA Medical Research Data (IMRD) UK
- The Netherlands – Integrated Primary Care Information (IPCI)

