7.1 Study Design

This is a descriptive cohort study using secondary data sources (electronic medical records) from eight databases in seven European countries reflecting either hospital or ambulatory care setting. The study population will be comprised of a cohort of diagCOVID-19 or labCOVID-19 patients in the database within the study time period.

Patients may be either diagnosed and followed-up in an outpatient or in an inpatient setting (according to the database) and they might be new users or prevalent users of systemic glucocorticoids. Based on these 2 characteristics, four mutually exclusive cohorts will be created overall. Not all cohorts can be constructed in each database. They will be used differently depending the objective as mentioned in the analysis section. An overview of the study design is provided in Figure 1 below.

Patients will be followed during the study period from COVID-19 diagnosis date to assess the utilization of systemic glucocorticoids specifically indicated for the treatment of COVID-19 and from treatment index date for the occurrence of outcomes of interest.

[figure not shown]

Figure 1 Study design

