Steroids often have adjusted dose regimens such that drug may be slowly increased or decreased over time and short acute treatment episodes are also possible. Such changes in dose over time will not be examined, however total cumulative dose will be examined in relation to outcomes of interest (see below).

Cumulative dose

For glucocorticoids used in COVID-19 indication, orally administered, if quantity is available, the formula to calculate the cumulative exposure in mg is described below:

$$Cumulative\ dose_{solid}[mg] = \sum_{all\ exposures} quantity \times amount_value [mg]$$

If the **quantity is missing**, the number of units per day for solid formulations are extracted. The cumulative exposure in mg can then be calculated using the following formula:

$$Cumulative\ dose_{solid}[mg] = \sum_{exposures} units\ per\ day \times amount_value [mg] \times duration$$

For intravenous administration (bolus administration), the dose administered each time will be counted.

$$Cumulative\ dose\ intravenous [mg] = \sum_{all\ exposures} amount_value [mg]$$

Exposure groups for incidence calculation (secondary objective 2 and 3)

For the incidence rates calculation, an on-treatment exposure will be considered with mutually exclusive groups to allow calculation of incidence rates.

Each person will be classified as belonging to one of the following mutually exclusive exposure groups at treatment index date following COVID-19 diagnosis:

- Use of systemic glucocorticoids without other treatments for COVID-19 (drug and respiratory support)
- Use of systemic glucocorticoids plus other treatments for COVID-19 (drug and respiratory support)
- Only other treatments and respiratory support with no systemic glucocorticoids

- No specific treatments for COVID-19 infection (other concomitant treatments for indications other than for COVID-19 are allowed)

A single prescription would be enough to consider the patient as exposed. See section 7.3.2.1 for description of 'other treatment for COVID-19' that are included.

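### Objectives 2 and 3 count from a glucocorticoid start, so the two groups without glucocorticoids have no defined time zero, and pre-treatment person-time is not clearly allocated

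*Protocol*

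**What the plan says.** Section 7.2.3 of the protocol offers two index dates only. One is diagnosis. The other is given as: "Treatment index date is defined as start of first systemic glucocorticoid treatment episode specifically for the treatment of COVID-19".

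Objectives 2 and 3 (Section 6.3) quantify outcomes within 30 and 90 days of the treatment index date. The Abstract agrees: "For secondary objectives 2 and 3 where the index date is based on treatment".

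Section 7.3.2.3 sets the classification rule: "Each person will be classified as belonging to one of the following mutually exclusive exposure groups at treatment index date following COVID-19 diagnosis". The third of the four groups is "Only other treatments and respiratory support with no systemic glucocorticoids" and the fourth is "No specific treatments for COVID-19 infection".

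Section 7.7.4 describes the denominator: "The crude person-time from relevant index date will be calculated for the following groups". It does not say which date is relevant for which group. It adds that only the earliest eligible treatment counts and that follow-up is censored at a switch. Section 7.7.5 takes propensity-score covariates from the 30 and 365 days before index. Section 7.3.2.1 lets a glucocorticoid qualify if started from 2 days before to 30 days after diagnosis.

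**The concern.** A person who never starts a glucocorticoid never reaches the only treatment index date that the protocol defines. Groups 3 and 4 consist of such people. Read literally, the rule for time zero fails for half of the groups whose rates are to be reported.

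A programmer must then choose a date. Diagnosis is the natural fallback, because it is the only other date defined. Combined with one group per person, that choice distorts the rates in opposite directions:

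- **Group 4** keeps the early events of patients who would have been treated later, but loses the event-free days of those who were. Its rate is too high.
- **Group 3** gains the days between diagnosis and the first drug, during which its members cannot have had the event, since they had to remain event-free to be treated. Its rate is too low.

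The glucocorticoid groups would meanwhile start up to 30 days later, so the four rates would not run on the same clock.

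**Working it through.** The protocol states no figure on this point, so there is nothing to reproduce. The check has two parts.

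**1. Does each group have a time zero?**

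| Group | Glucocorticoid start? | Date under 7.2.3 | Help from 7.7.4 |
|---|---|---|---|
| 1 Glucocorticoid alone | yes | yes | not needed |
| 2 Glucocorticoid plus other | yes | yes | not needed |
| 3 Other treatments only | never | none | first other drug is hinted at, not defined |
| 4 No specific treatment | never | none | none |

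Section 7.9.1 shows the same tension. It expects heavy censoring if glucocorticoids are often the second or third treatment, which presumes a clock that starts at any first treatment. Section 7.2.3 starts it at the glucocorticoid.

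**2. What would diagnosis as the substitute do?**

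Inputs:
- Event risk 3% or 26%, the case-fatality figures in Section 5.0. That these are 30-day risks is an assumption.
- Constant hazard h = −ln(1 − risk)/30, identical in all groups, so any difference between groups is artefact.
- Share q destined for treatment: 5, 20, 50 or 80% (assumed; not in the protocol).
- Treatment day T, assumed uniform over 0–10 days, exponential with mean 5 days capped at 30, or uniform over 0–30 days.

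*Group 4*, followed τ days from diagnosis, holds everyone never planned for treatment plus everyone with the event before T:
- events per patient: (1 − q)(1 − e^(−hτ)) + q·A, with A = E[1 − e^(−hT)]
- person-days per patient: (1 − q)(1 − e^(−hτ))/h + q·B, with B = E[(1 − e^(−hT))/h − T·e^(−hT)]

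Example with risk 26%, q = 20%, T uniform over 0–30, τ = 30:
- h = 0.010037, A = 0.1365, B = 1.298
- events = 0.8 × 0.26 + 0.2 × 0.1365 = 0.2353
- person-days = 0.8 × 0.26/0.010037 + 0.2 × 1.298 = 20.98
- rate = 11.21 per 1,000 patient-days against a true 10.04, a ratio of 1.117

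Ratio of group 4's rate to the truth at 30 days:

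| Risk | Treatment start | q = 5% | 20% | 50% | 80% |
|---|---|---|---|---|---|
| 3% | uniform 0–10 | 1.009 | 1.042 | 1.168 | 1.671 |
| 3% | exponential, mean 5 | 1.009 | 1.042 | 1.167 | 1.666 |
| 3% | uniform 0–30 | 1.026 | 1.124 | 1.495 | 2.950 |
| 26% | uniform 0–10 | 1.010 | 1.045 | 1.179 | 1.705 |
| 26% | exponential, mean 5 | 1.009 | 1.044 | 1.173 | 1.676 |
| 26% | uniform 0–30 | 1.025 | 1.117 | 1.452 | 2.583 |

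At 90 days the inflation is at most 1% (q = 5%), 1 to 5% (20%), 6 to 20% (50%) and 23 to 76% (80%). A simulation of 2,000,000 patients per scenario agreed at 30 days to within about two percentage points.

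*Group 3*, if also counted from diagnosis, with T now its first drug:
- events: E[e^(−hT) − e^(−hτ)]
- person-days: E[T·e^(−hT) + (e^(−hT) − e^(−hτ))/h]

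With risk 26%, T uniform over 0–30 and τ = 30, this is 0.1235/24.61 = 5.02 per 1,000, half the true rate. Over the three timing patterns the rate is understated by 17 to 50% at 30 days and 6 to 21% at 90 days.

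*Alternative.* Follow everyone from diagnosis as untreated and censor at T. Expected events then equal h times expected person-days, so the rate is unbiased in this model. In the simulation, the ratio of the treated rate to this untreated rate was 0.985 to 1.015.

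**The case against.** **The bias is not written into the plan.** The protocol nowhere says that groups 3 and 4 are followed from diagnosis. Section 7.7.4 speaks of types of person-time, counts events from the onset of each type, and censors at a switch. Read that way, untreated time could end at treatment start, and the artefact vanishes. This stands: the bias depends on a choice that the protocol leaves open. But the one-group-per-person wording of 7.3.2.3 points the other way, and neither reading supplies the missing dates.

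**The study is non-comparative.** Section 6.3 puts treated-versus-untreated comparison out of scope, 7.9.1 repeats this, and the Cox models run within groups. That limits the consequence. It does not remove it: each group's own rate is a deliverable, Section 7.7.8 refers to a reference group for incidence rates, and the checklist in Appendix 2 reports that a comparator is identified.

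**A several-fold distortion might be inferred.** A factor of about five or six arises only if some 10% of untreated patients start treatment each day, which means 1 − e^(−0.1 × 30) = 95% treated by day 30. Nothing in the protocol supports such uptake.

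**A reader might also infer that the cohorts overlap.** The hospital criterion "Are hospitalized 30 days prior or after diagnosis index date" seems to clash with "four mutually exclusive cohorts will be created overall" and to make eligibility depend on the future. But Section 7.2 assigns setting by data source type and treats a later admission of an ambulatory patient as an outcome. The Abstract lists SIDIAP, the one linked database, as ambulatory, and Section 7.5 names a single database with hospitalized patients. That database holds in-patient care, and nothing shows that diagnosis often precedes admission there. Neither inference is supported.

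**Conclusion.** The definitional fault is certain. Section 7.2.3 fixes a treatment index date that groups 3 and 4 cannot have, while 6.3, 7.3.2.3 and 7.7.5 require one for every person. This is a stated rule that fails, not detail left to a statistical analysis plan.

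The bias is conditional on using diagnosis as time zero with person-level groups. Given that choice, equal hazards and the assumed treatment timing, group 4's 30-day rate is inflated by about 1 to 3% at 5% uptake, 4 to 12% at 20% and 17 to 50% at 50%, and by more only at very high uptake. Group 3's rate is understated by 17 to 50%. In this model the glucocorticoid groups' own rates, counted from drug start, are not biased. If ambulatory uptake is low, the effect on group 4 may be only a few percent. Confounding by severity is a separate matter, which Section 7.9.1 already acknowledges.

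**What to change.** In Sections 7.2.3, 7.3.2.3 and 7.7.4, define time zero for each group and classify person-time instead of persons:

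- **Untreated person-time** runs from the diagnosis index date for everyone and is censored at the first qualifying COVID-19 treatment.
- **Treated person-time** starts at that treatment, or at diagnosis if the treatment began in the 2 days before it, with its own 30- and 90-day clock.
- **The group 3 index date** is the first other COVID-19 treatment newly started in the qualifying window around diagnosis. Without the words newly started, a continuing statin, antihypertensive or antidiabetic from Appendix 3 would set the date.
- **The covariate windows of 7.7.5** refer to the same group-specific dates.

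The cost is protocol wording and a person-time split in the code; no new data are needed. The downside is that a patient may contribute person-time to more than one group, so group counts no longer add up to distinct patients, and the tables should say so.
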